6.3 Dose Modification and Dose Interruption

6.3.1 Dose Modification and Management Guidelines for Rash

Two types of rashes may be seen with the GSK1120212 (trametinib) + GSK2141795 combination:

- 1. Acneiform, typically associated with MEK inhibitor therapy (trametinib).
- 2. *Maculopapular*, often associated with pruritus (GSK2141795).

If the diagnosis is unclear, a biopsy and photographs should be obtained as well as a dermatology consult. In addition, if the investigator thinks the rash is not consistent with a MEK inhibitor-associated acneiform rash and is \geq Grade 2, a skin punch biopsy should be performed.

In general, topical and oral antibiotics (doxycycline or minocycline) play a larger role in management of the MEK inhibitor acneiform rash, while topical and oral steroids are more relevant to the management of the AKT inhibitor maculopapular rash.

Rash prophylaxis is recommended for the first 6 weeks of study treatment.

Subjects should contact the investigator immediately upon onset of a rash. Full supportive care should be provided to subjects who experience a rash while on study.

The following information is a guideline. The investigator's best medical judgment should determine medical intervention for rash.

General Considerations in Rash Management

- Encourage subjects to avoid unnecessary exposure to sunlight.
- Employ a proactive approach (i.e., prophylactic treatment; see below for recommendations).
- If subject develops rash, verify treatment intervention and follow steps outlined below

Prophylactic Treatment (during the first 6 weeks of treatment)

The exact prophylactic regimen should be based on the investigator's experience; however, the following regimen is recommended:

- Broad-spectrum sunscreen (containing titanium dioxide or zinc oxide) with a skin protection factor (SPF) ≥15.
- Thick, alcohol-free emollient cream (e.g. glycerine and cetomacrogol cream) on dry areas of the body.

Reactive Rash Management

It is strongly recommended that subjects who develop rash or skin toxicities receive evaluations for management of the specific side effect.

- Upon the first signs of rash, mild strength topical steroid (e.g. hydrocortisone 1% cream) with escalation to higher strength and/or oral steroid as detailed below.
- Upon the first signs of papulopustular (acneiform) rash consider doxycycline (100 mg BID) or minocycline (100 mg BID).
- For pruritic lesions, the use of cool compresses and oral antihistamine agents may be helpful. Hypoallergenic moisturizers and emollients for dry skin (5% to10% urea in cetomacrogel cream or soft paraffin) may also provide symptomatic relief for pruritus.
- For **fissuring**, the use of Monsel's solution, silver nitrate, or zinc oxide cream is advised.
- For **desquamation**, thick emollients and mild soap are recommended.
- For **paronychia**, antiseptic bath and local potent corticosteroids in addition to oral antibiotics are recommended and, if no improvement is seen, a dermatology or surgery consultation is recommended.
- For **infected lesions**, bacterial and fungal culturing followed by the appropriate culture-driven systemic or topical antibiotics is indicated.
- For subjects who had study drug reduced because of rash, re-escalation may be considered if toxicity does not recur with a re-challenge at a lower dose.
- Consider the following algorithm (Table below) in a stepwise manner.

Rash Management Guidelines		
Rash Grading	Management of Rash	Study Drug(s) Dose Adjustment
Grade 1	Initiate Reactive Rash Management regimen Reassess after 2 weeks; if rash worsens or does not improve, proceed to step 2	Continue current dose.

Rash Management Guidelines		
Rash Grading	Management of Rash	Study Drug(s) Dose Adjustment
Grade 2	Initiate Reactive Rash Management regimen if not already started, but using moderate strength topical steroids.*	Continue current dose.
	Reassess after 2 weeks; if rash worsens or does not improve, proceed to step 3	
	Initiate Reactive Rash Management regimen if not already started, but using moderate strength topical steroids PLUS methyprednisolone dose pack.	Hold study treatment until rash improves to < Grade 2 (or resolves), then reduce dose of study medications by at least 25% and monitor for change in rash severity*. Reassess after 2 weeks; if rash worsens or does not improve, discontinue treatment.
> Grade 3	For papulopustular (acneiform) rash consider doxycycline 100 mg bid or minocycline 100 mg bid. Consider obtaining dermatology consultation. Manage rash per dermatologist's recommendation.	*For first occurrence of Grade 3 rash: restarting at the original dose may be considered after instituting optimal rash management.

6.3.2 Dose Modification and Management Guidelines for Diarrhea

Episodes of diarrhea have occurred in patients receiving trametinib (Investigator's Brochure, 2012a). Other frequent causes of diarrhea including concomitant medications (*e.g.*, stool softeners, laxatives, antacids, *etc.*), infections by *Clostridium difficile* or other pathogens, or partial bowel obstruction should be excluded.

Management and Dose Modification Guidelines for Diarrhea		
CTCAE Grade	Adverse Event Management	Action and Dose Modification
Uncomplicated Diarrhea, ¹ Grade 1 or 2	 Diet: Stop all lactose containing products; eat small meals, BRAT-diet (bananas, rice, apples, toast) recommended. Hydration: 8-10 large glasses of clear liquids per day (e.g., Gatorade or broth). Loperamide³: Initially 4 mg, followed by 2 mg every 4 hours or after every unformed stool; maximum 16 mg/day. Continue until diarrhea-free for 12 hours. Diarrhea >24 hours: Loperamide 2 mg every 2 hours; maximum 16 mg/day. Consider adding oral antibiotics. 	 Continue treatment. If diarrhea is grade 2 for > 48 h, interrupt GSK2141795 and trametinib (for up to 3 weeks) until diarrhea resolves to grade ≤1. Restart treatment at the same dose level If treatment delay is > 21 days, discontinue both agents. (Resumption of trametinib or GSK2141795 alone may be considered based on toxicity-benefit consideration and after consultation with PI).

Management and Dose Modification Guidelines for Diarrhea		
CTCAE Grade	Adverse Event Management	Action and Dose Modification
	• Diarrhea >48 hours : Loperamide 2 mg every 2 hours; maximum 16 mg/day. Add budesonide or other second-line therapies (octreotide, or tincture of opium) and oral antibiotics.	
Uncomplicated Diarrhea, ¹ Grade 3 or 4 and Any Complicated Diarrhea ²	 Clinical evaluation mandatory. Loperamide³: Initially 4 mg, followed by 2 mg every 4 hours or after every unformed stool; maximum 16 mg/day. Continue until diarrhea-free for 12 hours. Oral antibiotics and second-line therapies if clinically indicated Hydration: Intravenous fluids if clinically indicated. Antibiotics (oral or intravenous) if clinically indicated. Intervention should be continued until the subject is diarrhea-free for ≥24 hours. Intervention may require hospitalization for subjects at risk of 	 Interrupt BOTH agents until diarrhea resolves to ≤ grade 1. Restart with trametinib or GSK2141795 reduced by one dose level (for the combination, reduce both agents by one level).⁴ If more than one dose reduction of study treatment is clinically indicated, permanently discontinue treatment. If treatment delay is >21 days, discontinue treatment. (resumption of trametinib or GSK2141795 alone may be considered based on toxicity-benefit consideration and after consultation with PI)
1 Uncomplicat	life-threatening complications.	matems such as gramping, house a homiting >
 Uncomplicated diarrnea defined by the absence of symptoms such as cramping, hausea/vomiting, ≥ grade 2, decreased performance status, pyrexia, sepsis, neutropenia ≥ grade 3, frank bleeding, and/or dehydration requiring intravenous fluid substitution. Complicated diarrhea defined by the presence of symptoms such as cramping, nausea/vomiting, ≥ grade 2, decreased performance status, pyrexia, sepsis, neutropenia ≥ grade 3, frank bleeding, and/or grade 2, decreased performance status, pyrexia, sepsis, neutropenia ≥ grade 3, frank bleeding, and/or grade 2, decreased performance status, pyrexia, sepsis, neutropenia ≥ grade 3, frank bleeding, and/or 		
dehydration 3. Loperamide	dehydration requiring intravenous fluid substitution.3. Loperamide should be made available prior to start of study treatment so loperamide administration	
4. Escalation of with the PI a subsequent	 Escalation of trametinib and/or GSK2141795 to previous dose level(s) is allowed after consultation with the PI and in the absence of another episode of complicated or severe diarrhea in the 4 weeks subsequent to dose reduction. 	

6.3.3 GSK2141795 Dose Modification and Management Guidelines for Hypo- or Hyperglycemia

Hyperglycemia has been associated with treatment with GSK2141795.

Management and Dose Modification Guidelines for Hypo- or Hyperglycemia			
Criteria	Management Guidelines	Study Drug Modification	
(For management purposes, r reporting use NCI-CTCAE version	(For management purposes, refer to mild, moderate and severe intensity criteria; however for eCRF reporting use NCI-CTCAE version 4.0 Grades 1-5)		
Mild Fasting blood glucose > 150mg/dL	Monitor fasting and preprandial glucose.	Continue study drug	
Moderate to Severe Fasting blood glucose <70 mg/dL OR any blood glucose > 250mg/dL	 If a blood glucose >250 mg/dL, monitor for ketoacidosis as clinically indicated. When managing hyperglycemia associated with GSK2141795, be aware that the action of insulin or other antihyperglycemic agents (e.g., sulfonylureas, biguanides, etc.) may be substantially blocked by the study agent. However the action of antihyperglycemic agents would be restored as GSK2141795 is cleared. The patient should be observed closely for rebound hypoglycemia as GSK2141795 is held/or discontinued. Intravenous insulin treatment is recommended. 	Hold GSK2141795 and notify investigator immediately. The investigator should discuss intervention and possible resumption of GSK2141795 with the PI.	

6.3.4 Dose Modification and Monitoring Guidelines for LVEF Decrease

Decreases of the left ventricular ejection fraction (LVEF) have been observed in patients receiving trametinib. GSK2141795 dose is to be modified the same as for trametinib. ECHOs must be performed in regular intervals outlined in the Study Calendar. The same procedure (either ECHO or MUGA, although ECHO is preferred) should be performed at baseline and at follow-up visit(s).

Dose Modification Guidelines and Stopping Criteria for LVEF Decrease		
Clinical Assessment LVEF-drop (%) or		Action and Dose
	CTCAE grade	Modification
Asymptomatic	Absolute decrease of >10% in LVEF	• Hold trametinib and GSK2141795.
	compared to baseline and ejection	 Repeat ECHO in 2 weeks^a
	fraction below the institution's LLN.	• If the LVEF recovers within 4
		weeks (defined as LVEF ≥ LLN and
		absolute decrease ≤10%
		compared to baseline)
		\circ Consult with the GSK medical
		monitor and request approval
		for restart
		\circ Restart treatment with
		trametinib reduced dose by
		one dose level ^b
		\circ Repeat ECHO/MUGA 2, 4, 8
		and 12 weeks after re-start;
		continue in intervals of 12
		weeks thereafter
		 If LVEF does not recover within 4
		weeks
		 Consult with cardiologist
		 Permanently discontinue
		trametinib
		 Repeat ECHO/MUGA after 2, 4,
		8, 12, and 16 weeks or until
		resolution
		• Consult with principal
		investigator and GSK medical
Comparts and the C	- Cue de 2: mentione LV/EE 20, 200/ em 2, 200/	monitor ^e
Symptomatic	• Grade 3: resting LVEF 39-20% or >20%	Permanently discontinue
	absolute reduction from baseline	trametinib and GSK2141795
	• Grade 4: Resting LVEF $\leq 20\%$.	• Report as SAE
		• Consult with cardiologist
		• Repeat ECHO after 2, 4, 8, 12 and
16 weeks or until resolution.		
[•] If ECHO/MUGA does not show LVEF recovery after 2 weeks, repeat ECHO/MUGA 2 weeks later.		
* Escalation of trametinib to previous dose level can be considered if LVEF remains stable for 4 weeks		
arter restarting of trametinib. Approval from GSK Medical Monitor is required.		
and edema		

If LVEF recovers (defined as greater than or equal to LLN AND absolute decrease is less than or equal to 10% compared to baseline) at any time during the next 4 weeks, **after consultation with the PI**, both trametinib and GSK141795 can be restarted at a reduced dose. Monitoring LVEF will be performed 2 and 4 weeks after re-challenge, and every 4 weeks thereafter for 12 weeks and then by protocol

Copies of all cardiology consultations performed on subjects who experience a > 10% decrease in LVEF from baseline and whose cardiac ejection fraction is below the institution's LLN may also be required by GSK for review.

6.3.5 Dose Modification and Monitoring Guidelines for Liver Chemistry Changes

Liver chemistry stopping criteria are defined as follows:

When any of the liver chemistry stopping criteria are met, immediately discontinue trametinib and GSK2141795, perform liver event follow-up assessments, and monitor the patient until liver chemistries resolve, stabilize, or return to baseline values.

- ALT ≥ 3 × institutional ULN and bilirubin ≥2x institutional ULN (>35% direct bilirubin) (or ALT ≥3x institutional ULN and international normalized ratio [INR]
 >1.5x institutional ULN, if INR measured). NOTE: If serum bilirubin fractionation is not immediately available, treatment should be discontinued if ALT ≥ 3 × institutional ULN and bilirubin ≥2x institutional ULN. Serum bilirubin fractionation should be performed if testing is available. If testing is unavailable, record presence of detectable urinary bilirubin on dipstick, indicating direct bilirubin elevations and suggesting liver injury.
- ALT \geq 5 × institutional ULN.
- ALT \geq 3 × institutional ULN if associated with the appearance or worsening of symptoms of hepatitis or hypersensitivity such as fatigue, nausea, vomiting, right upper quadrant pain or tenderness, fever, rash, or eosinophilia.
- ALT \geq 3 × institutional ULN persisting for \geq 4 weeks.
- ALT \geq 3 × institutional ULN and cannot be monitored weekly for 4 weeks.

Liver chemistry threshold stopping criteria have been designed to assure subject safety and to evaluate liver event etiology during administration of investigational product and the follow-up period, and are in alignment with the FDA premarketing clinical liver safety guidance

(http://www.fda.gov/downloads/Drugs/GuidanceComplianceRegulatoryInformation/Guid ances/UCM174090.pdf). These procedures do not apply if subjects develop liver chemistry abnormalities as a result of progressive disease:

- Immediately withdraw the subject from study treatments.
- Notify NCCN within 24 hours of learning of the abnormality to confirm the subject's study treatment cessation and follow-up.

- Complete the "Safety Follow-Up Procedures" listed below.
- Complete the liver event case report forms. If the event also meets the criteria of an SAE (see Section 11.1.2), the SAE data collection tool will be completed separately with the relevant details.
- Upon completion of the safety follow-up, investigator to decide whether to
 permanently withdraw the subject from the study. Approval by the study PI for
 restarting IP can be considered where the subject is receiving compelling benefit and
 no effective alternative therapy is available OR liver chemistries have a clear
 underlying cause (*e.g.* biliary obstruction, hypotension) and liver chemistries have
 improved to normal or within 1.5x baseline and ALT < 3x institutional ULN).
 Subjects approved by the study PI for restarting IP must return twice a week for
 liver chemistries until stable, and then resume routine lab monitoring as per protocol.

Restarting IP: If requested by the investigator, drug restart /rechallenge following liver events that are possibly related to investigational product may be considered only for subjects who are already receiving compelling benefit from a critical or life-saving drug for whom there is no alternative treatment. In these cases, approval by the study PI for restart may be approved when the following conditions are satisfied:

- Ethics Committee or Institutional Review Board approval of drug restart/rechallenge must be obtained before IP can be administered.
- If the restart/rechallenge is approved by the study PI in writing, the subject must be provided with a clear description of the possible benefits and risks of drug administration, including the possibility of recurrent, more severe liver injury or death.
- The subject must also provide signed informed consent specifically for the IP restart/rechallenge. Documentation of informed consent must be recorded in the study chart.
- Study drug must be administered at the dose specified by the study PI.

Safety Follow-Up Procedures for subjects with $ALT \ge 3x$ institutional ULN and $\ge 2 \times$ value at Screening:

- Make every reasonable attempt to have subjects return to the clinic within 24 to 72 hours for repeat liver chemistries, additional testing.
- Monitor subjects at least weekly until liver chemistries (ALT, AST, alkaline phosphatase, bilirubin) resolve, stabilize or return to within baseline values.

Safety Follow-Up Procedures for subjects with $ALT \ge 3 \times institutional$ **ULN and bilirubin** $\ge 2 \times institutional$ **ULN (or** $ALT \ge 3 \times institutional$ **ULN and INR1** > 1.5):

• This event is considered an SAE (see Section 11.1.2). Serum bilirubin fractionation should be performed if testing is available. If fractionation is unavailable, urinary

bilirubin is to be measured via dipstick (a measurement of direct bilirubin, which would suggest liver injury).

- Make every reasonable attempt to have subjects return to the clinic within 24 hours for repeat liver chemistries, additional testing, and close monitoring (with specialist or hepatology consultation recommended).
- Monitor subjects twice weekly until liver chemistries (ALT, AST, alkaline phosphatase, bilirubin) resolve, stabilize or return to within baseline values.

In addition, for all subjects with no evidence of malignant involvement of the liver and $ALT \ge 3 \times institutional ULN$, every attempt must be made to also obtain the following:

- Obtain viral hepatitis serology testing including:
 - Hepatitis A IgM antibody.
 - Hepatitis B surface antigen and Hepatitis B Core Antibody (IgM).
 - Hepatitis C RNA.
 - Cytomegalovirus IgM antibody.
 - Epstein-Barr viral capsid antigen IgM antibody (or if unavailable, obtain heterophile antibody or monospot testing).
 - Hepatitis E IgM antibody
- Blood sample for analysis of serum creatine phosphokinase (CPK) and lactate dehydrogenase (LDH).
- Fractionate bilirubin, if total bilirubin $\geq 2x$ institutional ULN.
- Assess eosinophilia.
- Record the appearance or worsening of clinical symptoms of hepatitis, or hypersensitivity, fatigue, decreased appetite, nausea, vomiting, abdominal pain, jaundice, fever, or rash as relevant on the AE eCRF.
- Record use of concomitant medications, acetaminophen, herbal remedies, other over the counter medications, or putative hepatotoxins on the Concomitant Medications eCRF.
- Record alcohol use on the Liver Events eCRF.

The following are required for subjects with ALT $\ge 3x$ institutional ULN and total bilirubin $\ge 2x$ institutional ULN ($\ge 35\%$ direct bilirubin; bilirubin fractionation required) or INR $\ge 1.5x$ institutional ULN, without evidence of biliary obstruction or progressive disease, but are optional for other abnormal liver chemistries:

- Anti-nuclear antibody, anti-smooth muscle antibody, and Type 1 anti-liver kidney microsomal antibodies.
- Serum acetaminophen adduct assay (quantifies potential acetaminophen contribution to liver injury, detectable by HPLC assay more than 1 week following acetaminophen use) [41]
- Only in those with underlying chronic hepatitis B at study entry (identified by positive hepatitis B surface antigen): quantitative hepatitis B DNA and hepatitis delta antibody.

- Liver imaging (ultrasound, magnetic resonance, or computerized tomography) to evaluate liver disease.
- The Liver Imaging and/or Liver Biopsy eCRFs are also to be completed if these tests are performed.

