3. PARTICIPANT SELECTION

3.1 Inclusion Criteria

Participants must meet the following criteria on screening examination to be eligible to participate in the study:

- **3.1.1** Participants must have histologically or cytologically confirmed cervical cancer which is now recurrent or metastatic and is refractory to curative therapy or established treatments. Histologic or cytologic confirmation of the original primary tumor is required. All histologic types of cervical origin are permitted.
- **3.1.2** All patients must have measurable disease as defined by RECIST 1.1. Measurable disease is defined as at least one lesion that can be accurately measured in at least one dimension (longest diameter to be recorded). Each lesion must be ≥ 10 mm when measured by spiral CT, MRI or caliper measurement by clinical exam; or ≥ 20 mm with conventional techniques. Lymph nodes must be ≥ 15 mm in short axis when measured by CT or MRI.
- **3.1.3** Prior Therapy:
 - Patients must have had one prior chemotherapeutic regimen for management of cervical carcinoma. Initial treatment may include chemotherapy, chemotherapy and radiation therapy, and/or chemotherapy as consolidation/maintenance therapy. Chemotherapy administered in conjunction with primary radiation as a radio-sensitizer will not be counted as a systemic chemotherapy regimen.
 - Patients are allowed to receive, but are not required to receive, one additional prior treatment regimen (including a single chemotherapeutic, a combination of chemotherapeutics, or biologic drugs such as bevacizumab) for management of their recurrent or persistent disease.
 - Patients must have NOT received any class of drugs targeted to the PI3K pathway (such has PI3K inhibitors or mTOR inhibitors) or RAS-ERK pathway for management of recurrent or persistent disease.
- **3.1.4** Age \geq 18 years. Because no dosing or adverse event data are currently available on the use of GSK1120212 and GSK2141795 in participants < 18 years of age, children are excluded from this study. Cervical cancer is very rare in the pediatric population.
- **3.1.5** Life expectancy of greater than 3 months.
- **3.1.6** ECOG performance status ≤ 2 (see Appendix A).
- **3.1.7** Participants must have normal organ and marrow function as defined below:
 - Absolute Neutrophil Count (ANC) \geq 1,500/mcL

- Platelets \geq 100,000/mcL
- Hemoglobin $\geq 9.0/dL$
- PT/INR and PTT $\leq 1.5 \times$ institutional ULN

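### Section 6.3.5 gives the INR limit in the ALT ≥ 3 × ULN liver rule three ways, so stopping, SAE status and work-up need not apply to the same patients

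*Combined protocol and SAP*

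**What the plan says.** All three statements are in Section 6.3.5 and all pair INR with ALT ≥ 3 × ULN.

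- **Stop rule.** The first stopping bullet sets the INR limit at ">1.5x institutional ULN, if INR measured". The action is: "When any of the liver chemistry stopping criteria are met, immediately discontinue trametinib and GSK2141795".
- **Follow-up and SAE rule.** The second follow-up heading gives the INR alternative as "ULN and INR1 > 1.5", with no multiple of ULN after the number. The first bullet beneath it reads "This event is considered an SAE (see Section 11.1.2"). Recall within 24 hours and twice-weekly monitoring follow.
- **Required work-up.** The autoimmune antibodies and other listed tests are mandatory at INR at or above 1.5 times "institutional ULN, without evidence of biliary obstruction or progressive disease", and optional otherwise.

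Section 3.1.7 sets the entry limit: "PT/INR and PTT $\leq 1.5 \times$ institutional ULN". Section 11.1.2, which the SAE bullet cites, names no INR limit. The Section 9 calendar lists coagulation tests at screening and Cycle 1 Day 1 only.

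**The concern.** The three statements read as parts of one rule. The stop instructions send the site to the follow-up procedures below them, and the second follow-up heading mirrors the first stop bullet: ALT with bilirubin, or ALT with INR. INR is already a ratio, so 1.5 and 1.5 × ULN are different limits unless the laboratory's ULN is 1.0.

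The limit bears on three things: immediate withdrawal of both drugs, SAE status (with reporting to the overall principal investigator within one business day under Section 11.4.1), and which tests are compulsory. Liver enzyme elevation is expected with this combination. Section 2.2.3 lists grade 2 AST and ALT elevation among the dose-limiting toxicities and reports AST elevation in 22% of patients. A multicenter trial needs one reading of such a rule even if it is seldom used.

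**Working it through.** **Inputs.** The limits are those in Sections 6.3.5 and 3.1.7. The plan states no derived figure to reproduce. The institutional ULN for INR is not given, so it is assumed here over 0.9 to 1.3.

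**Step 1: the gap between the stop limit and the SAE limit.** Stop limit = 1.5 × ULN; SAE limit = 1.5; gap = 1.5 × ULN − 1.5.

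| Assumed ULN | 1.5 × ULN | Gap to 1.5 | INR values on which the two rules disagree |
|---|---|---|---|
| 0.9 | 1.35 | −0.15 | above 1.35 up to 1.50: stop limit met, SAE limit not met |
| 1.0 | 1.50 | 0 | none |
| 1.1 | 1.65 | +0.15 | above 1.50 up to 1.65: SAE limit met, stop limit not met |
| 1.2 | 1.80 | +0.30 | above 1.50 up to 1.80: same direction |
| 1.3 | 1.95 | +0.45 | above 1.50 up to 1.95: same direction |

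**Step 2: the rules side by side at an assumed ULN of 1.2, with ALT ≥ 3 × ULN.**

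| INR | Stop (> 1.80) | SAE (> 1.5) | Work-up (≥ 1.80) | Within entry limit (≤ 1.80) |
|---|---|---|---|---|
| 1.50 | no | no | no | yes |
| 1.60 | no | yes | no | yes |
| 1.75 | no | yes | no | yes |
| 1.80 | no | yes | yes | yes |
| 1.85 | yes | yes | yes | no |

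At 1.60 and 1.75 the event is an SAE with 24-hour recall, yet neither the INR stop limit nor the compulsory work-up applies. At exactly 1.80 the work-up applies and the stop limit does not; this comes only from the change from > to ≥. The last column shows that a patient can enroll with an INR already above 1.5. A rise in ALT alone, with INR unchanged, would then meet the SAE rule.

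**Step 3: conditions for a real discordance when ULN is above 1.0.** No other stop criterion may apply. So:

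- the bilirubin criterion is not met;
- ALT is below 5 × ULN;
- there are no new or worsening symptoms of hepatitis or hypersensitivity;
- it is not a case of ALT at or above 3 times "institutional ULN persisting for" at least 4 weeks;
- weekly monitoring is possible.

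An INR must also have been measured, although none is scheduled after Cycle 1 Day 1.

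**Step 4: a related boundary.** The direct bilirubin share is above 35% in the stop rule and at or above 35% in the work-up rule. The two differ only at exactly 35%.

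**The case against.** The strongest reply is that the plain 1.5 is a slip in an abbreviated heading. The 1 attached to INR there may be a footnote mark whose text is not in the available copy. Every other INR limit in the protocol is a multiple of ULN, and the same heading also omits the direct bilirubin share. This may well be so, but nothing in the documents supplies the missing multiplier, so the heading has to be taken as it reads.

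A second reply is that the stop rule is clear by itself, that the section treats SAE status separately from stopping, and that a wider net for SAEs and monitoring than for stopping is legitimate. That is fair as far as it goes. But the section does not say the difference is intended, and with a ULN below 1.0 the SAE net is the narrower one.

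A third reply is rarity. On-treatment INR is unscheduled, and the symptom criterion would often stop treatment anyway: fatigue, nausea, vomiting and rash are on the common-event lists for both drugs (Sections 6.1.5 and 6.1.6). This stands and limits the size of the point.

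A reader might also infer that sites would stop drug at an INR of 1.5. The documents do not show this, because the follow-up heading contains no instruction to stop.

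**Conclusion.** The inconsistency is real and is in current text. One ALT-plus-INR trigger carries three limits, and the stop and SAE limits coincide only at an institutional ULN of exactly 1.0. Over the assumed ULN of 0.9 to 1.3 the gap runs from −0.15 to +0.45 INR units, with its direction depending on whether ULN is below or above 1.0. The consequence is conditional: it needs an INR inside the gap and, where ULN exceeds 1.0, no other stop criterion met. Few patients should be affected.

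A reader might infer that the toxicity results would rest on conflicting definitions. The documents do not support that: toxicity is graded by CTCAE version 4 and tabulated (Sections 14.1.3 and 14.2), and no planned analysis counts liver stops. The response endpoint, sample size and decision rule are unaffected. The point concerns consistent safety management and SAE reporting. The > versus ≥ differences are minor; the missing multiplier is the substance.

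**What to change.** Check the follow-up heading against its source, including any footnote to INR. Then either reconcile the stop rule, the follow-up and SAE rule and the work-up rule in Section 6.3.5 to one INR definition (absolute or a multiple of ULN) with one inequality, or state explicitly that the SAE and follow-up limit is meant to differ from the stop limit. Use one inequality for the direct bilirubin share as well. Check the result against the entry limit in Section 3.1.7, so that it is clear how a patient whose baseline INR already exceeds the chosen limit is to be handled. Which limit to adopt is for the sponsor's clinical team.

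The cost is a few wording changes in one section, with no added tests, visits or patients.
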